Importantly, we will explore the dyadic effects of couple members' simultaneous engagement in the MBSR intervention. In addition to using proper statistical techniques to understand the effects of MBSR on each partner's outcomes, we will examine partner influences. For each primary hypothesis, we will examine the secondary hypothesis that each partner's improvement in each health outcome (self-report physical health, stress, mindfulness, and metabolic syndrome composite biomarker score) will be associated with improvement in the other partner's health outcome. In addition, we will examine the effects of the intervention on both partners' relationship satisfaction. Showing that relationship satisfaction can be enhanced is an important goal on its own, but we may also find that health outcomes improve when relationship quality improves.

3. Research Plan:

Procedures

Forty couples (N=80) will participate in a baseline visit to have blood drawn, BMI and BP measured, and to complete questionnaires assessing demographics, contextual factors, and baseline primary outcomes. Couples will be randomized to the MBSR condition (n=20 couples/ 40 individuals) or the wait list control condition (n=20 couples). The baseline blood draws and survey administration will take place at the CSRU, with the HRU as back up as needed. The blood analysis will be done by the YCCI Core lab. All participants will receive an informational sheet about metabolic syndrome.

Participants will be randomized to the intervention or wait-list group after informed consent is obtained, the initial blood is drawn and survey baseline is completed at the CSRU. A random digit generator will be used that assigns a condition (in this case, intervention or wait list) to each couple ID number.

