Accounting for simultaneous participation of couple members in MBSR for manual development. Prior to recruitment, the team will meet with [name], the MBSR instructor to adapt the MBSR manual so that it accounts for couples participating in the classes. Although the MBSR curriculum will not be substantially altered from its validated form, [name] will provide suggestions about how each practice and assignment in the program can acknowledge the partner's presence. We will maintain the standard MBSR program so that it can be easily disseminated to the public in later phases of this research. We are not developing a new relationship oriented MBSR. Rather, we will provide instruction about how each assignment should be carried out knowing that the partner is also in the program at the same time. Upon completion of the study, we will obtain interventionist feedback about how couple participation may have altered the MBSR program. [name] will keep notes about the influence of couple dynamics in her classes throughout the study and summarize them in a team meeting with the PI, Co-Is, and Project manager every 4 weeks and at the end of the study.

Measurement Schedule

	# of items	Variable type	Recruit	Baseline assess	8-week assess
Recruitment					
Referral or chart review: Potential participant has 3 of the following? (a) Abdominal obesity: waist circumference >102 cm in men, >88 cm in women; (b) Hypertriglyceridemia: ≥ 150 mg/dL (1.69 mmol/L); (c) Low high-density lipoprotein (HDL) cholesterol: <40 mg/dL (1.04 mmol/L) in men, <50 mg/dL (1.29 mmol/L) in women; (d) High blood pressure (BP): $\geq 130/85$ mm Hg and/or taking BP medication; (e) High fasting glucose: ≥ 110 mg/dL (≥ 6.1 mmol/L).	1	Inclusion criteria	X		
Participant is 60 or over.	1	Inclusion criteria	X		
Participant married or in romantic relationship?	1	Inclusion criteria	X		
Are they living together?	1	Inclusion criteria	X		
Participant's partner interested in being in the study?	1	Inclusion criteria	X		
Both partners age 60 or over?	1	Inclusion criteria	X		
Either partner non-English speaking?	1	Exclusion criteria	X		
Either partner practice mind-body therapies more than once/week (yoga, meditation)?	1	Exclusion criteria	X		
Either partner taking psychiatric medications?	1	Exclusion criteria	X		
Random assignment to intervention or waitlist control group	1	Intervention/control status			

Self-report Measures (Both partners)					
Socio demographics: age, gender, education, income	4	Covariates		X	X

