Feasibility outcomes will be observed, recorded, and qualitatively evaluated. Descriptive characteristics of the cohort will be summarized with means and standard deviations and counts and percentages according to intervention group. Although this pilot study will not be powered to test all outcomes for statistical significance, the primary quantitative outcomes are expected to have continuous Gaussian distributions making possible the comparison of intervention and control group results with linear mixed effects regression models that can accommodate the clustering of outcome results within couples. Finally, in anticipation of future studies of the metabolic syndrome outcome,

selected analyses will be conducted to compare the utility of the composite metabolic syndrome outcome and with a version of this outcome yielded by a measurement model in a structural equation modeling context.

Hypothesis 1: Self-reported physical health will be greater on average for participants in the MBSR intervention group compared to a wait-list control group. A multivariable linear mixed effects model will be used to assess whether self-reported physical health is greater in the intervention group than in the control group. A random effect will be used to account for the clustering of outcome values within couples. A pre-specified set of covariates will be entered into the regression model including baseline self-reported physical health and demographics and contextual factors that differ significantly across intervention and control groups. Model goodness of fit will be assessed with residual analysis, influence statistics, and goodness-of-fit statistics.

Hypothesis 2: MBSR will reduce each partner's self-reported stress and increase their mindfulness. The analyses for these two secondary outcomes will proceed according to the same procedures as cited for Hypothesis 1 above.

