How quantitative and qualitative data will be combined to understand outcomes. Qualitative data will be analyzed using Atlas.ti software and themes will be identified regarding partner influence on study experience. Key demographic characteristics and results from quantitative questions regarding decision making in participation and adherence will be entered into the software as coded attributes. Queries will be conducted to investigate the relationships between identified themes and coded attributes. Finally, the results of this qualitative analysis will be used to formulate hypotheses about the meanings and mechanisms underlying the quantitative results for Hypotheses 1 and 2, and especially, for the results of dyadic analyses of couple members' simultaneous engagement in the MBSR intervention.

Power: The sample size procedure in PASS shows that in anticipation of loss-to-follow-up, and with recognition of dependency in results from couples, the effective sample size is estimated to be 70, a reduction of 10 from the enrollment of 80 study participants. Assuming power of 80%, an outcome standard deviation of 10, and equal assignments to the intervention and control groups, this effective sample size will allow for detection of a difference between intervention and control groups mean values for the SF-12 outcome of 6.43 or more at the two-sided level of significance of 0.05. The sample size procedure in PASS was performed.

SECTION III: RECRUITMENT/CONSENT AND ASSENT PROCEDURES

1. Targeted Enrollment: Give the number of subjects: 80 participants

- a. Targeted for enrollment at Yale for this protocol: 80
- b. If this is a multi-site study, give the total number of subjects targeted across all sites: N/A

2. Indicate recruitment methods below. Attach copies of any recruitment materials that will be used.

- | | | |
|---|---|-------------------------------------|
|  Flyers |  Internet/Web Postings |  Radio |
|  Posters |  Mass E-mail Solicitation |  Telephone |
|  Letter |  Departmental/Center Website |  Television |
|  Medical Record Review* |  Departmental/Center Research Boards |  Newspaper |

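### The covariates for Hypotheses 1 and 2 are called pre-specified but are partly chosen by significance tests between the randomised arms

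*Protocol*

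**What the plan says.** The Hypothesis 1 paragraph of Section I, item 13 (Statistical Considerations) opens the covariate rule with "A pre-specified set of covariates will be entered into the regression model including baseline self-reported physical health" and completes the same sentence with "demographics and contextual factors that differ significantly across intervention and control groups". It gives no significance level, no test and no list of contextual factors. For perceived stress and mindfulness, the Hypothesis 2 paragraph says: "The analyses for these two secondary outcomes will proceed according to the same procedures as cited for Hypothesis 1 above".

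Three other places bear on this:

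- **Procedures (Section I, item 3), timing of measurement.** Couples attend a baseline visit "to complete questionnaires assessing demographics, contextual factors, and baseline primary outcomes".
- **Procedures, randomisation.** It takes place "after informed consent is obtained, the initial blood is drawn and survey baseline is completed at the CSRU", and the generator "assigns a condition (in this case, intervention or wait list) to each couple ID number".
- **Measurement Schedule.** The row "Socio demographics: age, gender, education, income" carries the variable type of covariate, with no condition attached.

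No other part of the protocol gives a fixed covariate list that would override the rule in item 13.

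**The concern.** The sentence contradicts itself. A set is pre-specified if it can be written down before the arms are compared, and this one can be written down only afterwards.

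The criterion is also the wrong one. These variables are measured before couples are randomised, so a significant difference between arms can only reflect chance allocation. In a randomised comparison, the reason to adjust is that a variable predicts the outcome, and a baseline p-value does not measure that. The rule can admit a useless variable and leave out a strongly prognostic one that happened to balance.

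Two things are at stake. The model behind the primary treatment estimate is not fixed until trial data have been examined, and with no stated test, level or candidate list the analyst has discretion. The rule may also give up precision that a fixed prognostic adjustment would have secured.

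**Working it through.** **The plan's own figure.** The simulation below borrows its effect size from the Power paragraph: "mean values for the SF-12 outcome of 6.43 or more at the two-sided level of significance of 0.05", with SD 10 and an effective sample of 70. At 35 per arm the normal formula gives (1.960 + 0.842) × 10 × √(2/35) = 6.70, so 6.43 does not reproduce; it corresponds to 38 per arm. That is a separate matter. Here 6.43 serves only as an illustrative effect, and the conclusion does not depend on it.

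**Inputs from the protocol.** 20 versus 20 couples; four named demographics; difference 6.43; SD 10.

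**Assumptions, because the protocol gives no values.** Selection at the 0.05 level; independent candidates; within-couple correlation 0.5 (0.3 as an alternative); baseline-outcome correlation 0.6; no loss to follow-up.

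**Step 1: how often the rule changes the model.** Under randomisation, P(at least one of k selected) = 1 − 0.95^k.

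| k | Probability |
|---|---|
| 1 | 0.050 |
| 2 | 0.098 |
| 3 | 0.143 |
| 4 | 0.185 |

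If the filter covers the demographics, k is 4, or 3 if gender cannot differ between arms (as in husband-wife couples). If it covers contextual factors only, k is unknown. These figures assume couple-level tests. Tests that ignored the pairing of partners would select at least one of four in about 30% of trials at a within-couple correlation of 0.3, and 38% at 0.5.

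**Step 2: the effect on the couple-mean scale.** The SD of a couple mean is 10 × √((1 + ρ)/2).

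- ρ = 0.5: SD 8.66, so 6.43/8.66 = 0.742.
- ρ = 0.3: SD 8.06, so 6.43/8.06 = 0.798.

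**Step 3: power and type I error.** The model is a couple-mean analysis of covariance, with 40,000 simulated trials per setting. The outcome is 0.6 × baseline + c × (X1 + X2) + effect + error, with residual variance 0.64 − 2c². There are four candidates, of which X1 and X2 are prognostic with coefficient c. The baseline outcome is always in the model. Power at effect 0.742:

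| Covariates besides the baseline outcome | c = 0 | c = 0.10 | c = 0.20 | c = 0.35 |
|---|---|---|---|---|
| Chosen by the rule | 0.787 | 0.793 | 0.795 | 0.807 |
| None | 0.800 | 0.804 | 0.802 | 0.802 |
| One prognostic, fixed | 0.787 | 0.798 | 0.815 | 0.867 |
| Two prognostic, fixed | 0.775 | 0.794 | 0.829 | 0.934 |
| One non-prognostic, fixed | 0.788 | 0.793 | 0.791 | 0.790 |
| Two non-prognostic, fixed | 0.775 | 0.780 | 0.777 | 0.779 |

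At effect 0.798 the pattern is the same:

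- Rule: 0.848/0.850/0.852/0.862.
- Baseline outcome alone: 0.858/0.860/0.858/0.858.
- Two prognostic covariates fixed: 0.838/0.850/0.883/0.960.

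Across both effects, the rule minus the baseline outcome alone runs from −1.3 to +0.5 percentage points. Type I error under the rule is 0.053/0.050/0.049/0.041 (Monte Carlo standard error 0.001), so it is not inflated; it becomes conservative when the covariates are strongly prognostic.

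**Scale of c.** X1 and X2 together explain 2c²/0.64 of the variance left after baseline: 3% at c = 0.10, 12.5% at 0.20 and 38% at 0.35.

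**The case against.** - **The sentence has a milder reading.** The significance condition may attach only to contextual factors, with the demographics always entered. The unconditional covariate label in the Measurement Schedule fits that. This stands as a reading, and under it the power figures above do not apply. The contextual factors, which the protocol never lists, would still be selected by significance. Two readings that give different primary models are themselves a reason to rewrite the sentence.
- **The harm is small.** This stands. Type I error is safe, and the baseline outcome, plausibly the strongest predictor, is always in the model. Moving from the rule to the baseline outcome alone changes power by about one point at most, so that version of the fix buys a fixed model rather than power.
- **The comparison with two prognostic covariates assumes one knows which two matter.** This also stands. Fixing all four candidates (8,000 trials per setting, effect 0.742) gives 0.76/0.77/0.81/0.92 against 0.80/0.79/0.81/0.80 for the rule: worse when prognosis is weak, level at c = 0.20, better only at 0.35. The 0.35 setting is a strong assumption with no support in the protocol. A long fixed list is therefore not the remedy.
- **Follow-up will not be complete.** With 17 versus 17 couples (an assumption), the rule's power falls to about 0.71–0.74. The absolute figures above are therefore optimistic; they serve to compare strategies.
- **The detail might be in a statistical analysis plan.** The protocol does not leave the matter open; it states a rule. A later plan would either inherit that rule or conflict with it.

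**Conclusion.** The concern holds and is minor. The protocol calls the covariate set fixed in advance and in the same sentence makes part of it depend on observed differences between randomised arms. That is true on either reading of the sentence, and Hypothesis 2 inherits it.

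If the filter covers the demographics, chance alone would change the primary model in about 14% to 19% of trials (independent candidates, couple-level tests at 0.05). Validity of the test is not threatened. The power cost is conditional. Against two fixed prognostic covariates it is nil at weak prognostic strength, about 3 points at c = 0.20 and about 13 points at c = 0.35 (effect 0.742). The rule offers no material advantage over the baseline outcome alone. The prognostic strengths, the baseline correlation and the within-couple correlation are all assumptions. In a feasibility pilot this calls for a wording correction, not a redesign.

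**What to change.** Replace the significance clause in the Hypothesis 1 paragraph with a closed list, and state that the same principle applies to Hypothesis 2. Deleting the clause alone is not enough, because that would leave all demographics and an unlisted set of contextual factors in the model. Either option is sound:

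1. Adjust for the baseline value of the outcome being analysed, and nothing else.
2. Adjust for that baseline value plus one or two variables already labelled as covariates in the Measurement Schedule and expected to be prognostic, such as age.

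Report baseline differences between arms descriptively, without using them to choose the model.

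The cost is one sentence, and all the variables are already collected. Option 1 has no material power cost against the present rule (at most about 0.5 points in the settings examined). Under option 2, each added covariate that proves non-prognostic costs about 1 point against the baseline outcome alone, and two cost 2 to 3 points.

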Physical health symptoms (SF-12)	12	Primary outcome		X	X
Perceived stress scale (Roberti et al., 2006)	10	Primary outcome		X	X
Kentucky Inventory of Mindfulness Skills (Baer et al., 2004)	39	Primary outcome		X	X
Relationship Assessment Scale (Hendrick, 1988)	7	Secondary outcome		X	X
Health behavior questionnaire (sleep, physical activity, eating behavior, medication adherence (Schulz et al., 1997))	22	Secondary outcome		X	X
Couples' decision making in participation and adherence: 1) How was your partner involved in your decision to first participate in the intervention? (Responses: a. encouraged you, b. discouraged you, c. neither) 2) How was your partner involved in your decision to continue with each class? (Responses: a. encouraged you, b. discouraged you, c. neither) 3) Open ended question: Describe how participating with your partner influenced your experience with the intervention.	3	Exploring couple dynamics			X
Biological Measures (Both partners)					
Blood draw: to assess hypertriglyceridemia and low high-density lipoprotein (HDL) cholesterol and high fasting glucose	3	Secondary outcome		X	X
Abdominal obesity- waist circumference per WHO protocol (2011)	1	Secondary outcome		X	X
Blood pressure (automated Carescape cuff)	1	Secondary outcome		X	X
Do both partners, only the husband, or only the wife have metabolic syndrome at baseline?	1	Exploring couple dynamics			
Feasibility Measures (Both partners)					
Percent of couples who screen versus enroll (Project manager keeps a record.)	1	Feasibility outcome	X		
# of MBSR sessions attended (Interventionist takes attendance.)	1	Feasibility outcome			X
Total minutes of home MBSR practice (Participants keep a daily record.)	1	Feasibility outcome			X

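### The measurement schedule labels perceived stress and mindfulness primary outcomes, the Hypothesis 2 analysis calls them secondary, and the rest of the protocol supports the SF-12 as the single primary

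*Protocol*

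**What the plan says.** **Outcome roles.** In the Measurement Schedule (Section I, item 3), the variable-type column reads "Physical health symptoms (SF-12) 12 Primary outcome" for the SF-12, "10 Primary outcome" for the perceived stress scale and "39 Primary outcome" for the mindfulness inventory; the figures are item counts. The same column marks relationship satisfaction, health behaviors and the biological measures as secondary.

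Section I, item 13, under Hypothesis 2, says of stress and mindfulness: "The analyses for these two secondary outcomes will proceed according to the same procedures as cited for Hypothesis 1 above".

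Elsewhere:
- Item 2, Aim 2, names self-reported physical health, measured by the SF-12, as the primary outcome, in the singular.
- Item 13, dyadic analysis, attaches the primary-outcome term to reports of health.
- Item 13, Power, gives a detectable difference of 6.43 for the SF-12 only, at two-sided 0.05.
- Item 3, Procedures, uses a plural: "to complete questionnaires assessing demographics, contextual factors, and baseline primary outcomes".
- The opening of item 13 also uses a plural: "the primary quantitative outcomes are expected to have continuous Gaussian distributions". The same sentence begins "Although this pilot study will not be powered to test all outcomes for statistical significance".

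**Visits.** The text on recruitment, data management and retention in item 3 has questionnaires at baseline, 8 weeks and 3 months. It places the 8-week visit 5 to 11 weeks after enrollment and the 3-month visit 10 to 14 weeks after enrollment. The schedule's last column is the 8-week assessment. The MBSR condition consists of eight weekly sessions.

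**The concern.** The protocol assigns a role to stress and mindfulness twice, in opposite ways. This is not detail left to a statistical analysis plan: a plan that followed either statement would contradict the other. The label decides which result can carry the trial's primary quantitative conclusion. A positive stress or mindfulness result could be reported as primary by citing the schedule, or as secondary by citing the analysis section, and that choice could be made after the data are seen. The Aim 3 background says much earlier MBSR research already supports Hypothesis 2, so a positive result there is quite likely.

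The visit point is separate and smaller. The dyadic analysis treats 8 weeks and 3 months as distinct time points. The windows let the two visits fall close together, and they let an end-of-course assessment take place before the course ends.

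**Working it through.** **1. Role statements side by side**

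| Place | SF-12 | Stress, mindfulness |
|---|---|---|
| Measurement Schedule | primary | primary |
| Item 2, Aim 2 | the primary outcome | not given that role |
| Item 13, Hypothesis 2 | – | secondary |
| Item 13, dyadic analysis | reports of health are primary | not named |
| Item 13, Power | powered | no power statement |

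The schedule uses both labels, so its primary cells are not a generic tag. Only the schedule explicitly makes stress and mindfulness primary. The two plurals fit several primaries but do not name them.

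The sentence in item 2 beginning "For each primary hypothesis, we will examine the secondary hypothesis" does not count as evidence of several primary outcomes. It contrasts main hypotheses with the partner-influence hypothesis, and its list includes the metabolic composite, which the aims call exploratory.

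**2. The plan's own figure**

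Inputs from Power: effective sample size 70 (35 per arm), SD 10, 80% power, two-sided 0.05. By the normal approximation, the detectable difference is 10 × √(2/35) × (1.960 + 0.842) = 6.70, not 6.43. A figure of 6.43 corresponds to 38 per arm: 10 × √(2/38) × 2.802 = 6.43. That mismatch is a separate matter. The statement is used here only to show which outcome was powered and that 0.05 was not divided.

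**3. Illustration of what the labels could mean**

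Assume that there is no true effect, that three two-sided tests are each done at 0.05, and that any one can support a primary claim.

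- Independent tests: 1 − 0.95³ = 0.143.
- Equal correlation ρ: 1 − ∫ [Φ((1.96 − √ρ·u)/√(1−ρ)) − Φ((−1.96 − √ρ·u)/√(1−ρ))]³ φ(u) du.

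| Assumed ρ | Chance of at least one false positive |
|---|---|
| 0 | 14.3% |
| 0.3 | 13.6% |
| 0.5 | 12.5% |
| 0.7 | 10.9% |

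The correlations and the any-one rule are assumptions, not protocol content.

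**4. Visit windows**

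- Overlap: weeks 5–11 and weeks 10–14 share weeks 10–11.
- Earliest course end: if session 1 falls on the day of enrollment, session 8 falls at 7 weeks. Any wait for a class to start makes it later.
- The window opens at week 5, so at least two weeks of it (7 − 5) precede the last session.

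**5. Visit for Hypothesis 1**

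The Hypothesis 1 text names no visit. The schedule gives the SF-12 one follow-up, at 8 weeks. The model takes baseline as a covariate and has a random effect for couple only, which suits one follow-up value per person. Both point to 8 weeks.

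**The case against.** The strongest reply is that the intent is clear. Every explicit role statement outside the schedule agrees that the SF-12 is the primary outcome, and the Hypothesis 2 model is the same under either label. The study is a pilot whose first aim is feasibility, and it says it is not powered for all outcomes. On this view two table cells are slips. Most of this stands: it limits the weight of the point and shows which way to correct. It does not remove the contradiction, because the schedule separates primary from secondary and still puts stress and mindfulness in the primary tier.

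A reader might go further and infer any of the following, none of which the documents support:

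- **The trial has three co-primary outcomes, or no identifiable primary.** Aim 2, the Hypothesis 2 text, the dyadic analysis and the power statement point to one.
- **The trial runs an 11% to 14% false-positive risk.** That needs a rule that any one of three tests suffices, and none is stated.
- **Weeks 10 to 11 make records unassignable.** Each visit has its own payment, and the 8-week visit has its own interview, so records would ordinarily be identified by visit. The problem is the spacing between visits.

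It is also fair that the visit points are not about outcome roles and add nothing to the weight of the label conflict.

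**Conclusion.** The contradiction is real, sits in current text and depends on no calculation. Two of the three primary labels in the schedule conflict with the analysis section. The protocol as a whole favors the SF-12 as the single primary quantitative outcome, so the labels should be corrected before results are known. The point is moderate: it governs how a stress or mindfulness result may be reported, not how it is analysed. The 11% to 14% figure is only an illustration under assumed correlations and an unstated decision rule.

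The separate visit point also holds. The windows overlap by one week, the first opens at least two weeks before the last session can take place, and the schedule omits the 3-month visit. The two-week figure assumes the first session falls on the day of enrollment, the most favorable case.

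**What to change.** **Outcome roles**
- Relabel perceived stress and mindfulness as secondary in the Measurement Schedule.
- Make the plural wording in Procedures and in the opening of Statistical Considerations agree with a single primary quantitative outcome, the SF-12 physical health score.
- Leave the reference to each primary hypothesis in the Background as it is.
- Report a positive stress or mindfulness result as secondary.

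**Visits**
- Set assessment windows that do not overlap, the first opening only after the last session, with the same timing for wait-list couples.
- Add the 3-month visit to the schedule and show which measures are taken then.
- State that the Hypothesis 1 comparison is at the post-intervention (8-week) visit.

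**Cost.** These are wording and table edits, with no change to sample size or model. One decision is needed: whether the biological measures are taken at 3 months, since the schedule places them only at baseline and 8 weeks. Stress and mindfulness lose the primary label, and the first visit window becomes somewhat narrower.
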